#### *Risk of contracting COVID-19 infection during study participation*

As long as the COVID-19 pandemic is ongoing, there is a risk of contracting a SARS-CoV-2 infection during the time period of study participation. Participants will be asked about

symptoms and risks of COVID-19 infection prior to each study visit and on the day of the study visit. Participants who are at high risk will be asked to have a COVID-19 test performed at a local public health lab and must have received a negative test prior to attending the study site. Participants will be asked further information regarding symptoms suggestive of COVID-19 infection as part of the screening visit and subsequent visits (as applicable in accordance with guidance from the relevant regional and local public health authorities). Participants must not have had a positive test within 2 weeks of the screening visit. If a participant received a COVID-19 positive test during study participation, the investigator will have to decide whether remaining in the study is compatible with participant’s and site personnel’s safety and well-being.

## **5.10. Visit schedule**

### *5.10.1. Pre-Study Screening and Baseline Evaluation*

***Prior to visit 1, all subjects will be provided with the Information Letter related to COVID-19 and asked to complete the Ontario Covid-19 Assessment Tool 24 hours and 1 hour prior to scheduled study visit.***

#### ***Visit 1: Screening***

Recruited patients will be invited to attend Visit 1 to undergo study screening. All subjects will undergo Ontario Covid-19 Assessment Tool and Information Letter. Patient eligibility will be assessed against the study inclusion/exclusion criteria and patients will undergo informed consent. Subjects who provide informed consent and are enrolled into the study will undergo screening procedures: complete medical history, physical examination, methacholine challenge, spirometry sputum induction, and blood sampling. Subjects will complete the Leicester Cough Questionnaire, the modified Borg Scale, and Cough Severity Visual Analogue Scale (VAS, 0-100mm) to assess severity and intensity of cough sensations including urge to cough, throat itch, throat tickle, and throat irritation. If the sputum quality obtained during the screening visit is deemed of poor quality, then the subject will be requested to repeat the sputum induction procedure within 14 days of visit 1 to ensure an adequate sample is obtained for assessment. Following the screening visit, subjects will be booked into the 8 remaining study visits and randomized into the intervention (mepolizumab) arm or placebo arm. Subjects will be scheduled to return for Visit 2 within 2 weeks of the screening visit.

#### *5.10.2. Treatment/Assessment Visits*

##### ***Visit 2: Baseline Cough Monitoring***

All subjects will undergo Ontario Covid-19 Assessment Tool and Information Letter prior to study visit. Enrolled subjects will wear an ambulatory cough monitor for 24 hours and be scheduled to return the following day for Visit 3.

##### ***Visit 3: Week 0 Administration of Mepolizumab/Placebo (1st Injection)***

All subjects will undergo Ontario Covid-19 Assessment Tool and Information Letter prior to study visit. Subjects will return with the cough monitor 24 hours following Visit 2. If no recording was obtained during the past 24 hours due to recording device malfunction (such as battery or card failure) then the subject will be asked to repeat the recording within 24-48 hours of prior attempt at recording. Subjects will undergo spirometry, sputum induction, and blood sampling and complete the Leicester Cough Questionnaire, the modified Borg Scale, and the Cough Severity VAS to measure the severity and intensity of cough sensations. Urine will be collected in WOCBP to screen for pregnancy. The first injection of mepolizumab/placebo will be administered in the clinical research facility by a study physician. The subject will be observed for a minimum of 1 hour for the appearance of any acute drug reactions.

##### ***Visit 4: Week 4 Administration of Mepolizumab/Placebo (2nd Injection)***

All subjects will undergo Ontario Covid-19 Assessment Tool and Information Letter prior to study visit. Subjects will return to the clinical research facility 4 weeks following Visit 3. Subjects will undergo blood sampling and complete the Leicester Cough Questionnaire, the modified Borg Scale, and the Cough Severity VAS. Urine will be collected in WOCBP to screen for pregnancy. The second injection of mepolizumab/placebo will be administered in the clinical research facility by a study physician. The subject will be observed for a minimum of 1 hour for the appearance of any acute drug reactions.

##### ***Visit 5: Week 8 Cough Monitoring and Administration of Mepolizumab/Placebo (3rd Injection)***

All subjects will undergo Ontario Covid-19 Assessment Tool and Information Letter prior to study visit. Subjects will return to the clinical research facility 4 weeks following Visit 4. Urine will be collected in WOCBP to screen for pregnancy. The third injection of mepolizumab/placebo will be administered in the clinical research facility by a study physician. The subject will be observed for a minimum of 1 hour for the appearance of any acute drug reactions. Subjects will wear an ambulatory cough monitor for 24 hours and be scheduled to return the following day for Visit 6.

#### ***Visit 6: Assessment of Blood, Sputum and Questionnaires***

All subjects will undergo Ontario Covid-19 Assessment Tool and Information Letter prior to study visit. Subjects will return with the cough monitor 24 hours following Visit 5. If no recording was obtained during the past 24 hours due to recording device malfunction or if the recording quality is deemed poor, then the subject will be asked to repeat the recording within 24-48 hours of prior attempt at recording. Subjects will undergo spirometry, blood sampling and sputum induction and complete the Leicester Cough Questionnaire, the modified Borg Scale, and the Cough Severity VAS.

#### ***Visit 7: Week 12 Administration of Mepolizumab/Placebo (4th Injection)***

All subjects will undergo Ontario Covid-19 Assessment Tool and Information Letter prior to study visit. Subjects will return to the clinical research facility 4 weeks following Visit 6. Subjects will undergo blood sampling and complete the Leicester Cough Questionnaire, the modified Borg Scale, and the Cough Severity VAS. Urine will be collected in WOCBP to screen for pregnancy. The fourth injection of mepolizumab/placebo will be administered in the clinical research facility by a study physician. The subject will be observed for a minimum of 1 hour for the appearance of any acute drug reactions.

#### ***Visit 8: Week 14 Cough Monitoring***

All subjects will undergo Ontario Covid-19 Assessment Tool and Information Letter prior to study visit. Subjects will wear an ambulatory cough monitor for 24 hours and be scheduled to return the following day for Visit 9.

***Visit 9: Final Visit: Assessment of Blood, Sputum and Questionnaires***

All subjects will undergo Ontario Covid-19 Assessment Tool and Information Letter prior to study visit. Subjects will return with the cough monitor 24 hours following Visit 8. If no recording was obtained during the past 24 hours due to recording device malfunction then the subject will be asked to repeat the recording within 24-48 hours of prior attempt at recording. Subjects will undergo spirometry, methacholine challenge, blood sampling and sputum induction and complete the Leicester Cough Questionnaire, the modified Borg Scale, and the Cough Severity VAS.

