#### 8.4. AEs of Study Procedures

Events that may be regarded as expected complications associated with the investigations are shown in the table below.

**Table 5.** Known complications associated with study procedures conducted in this study.

Procedure	Known complications
Spirometry	Cough, breathlessness
Blood Sampling	Fainting, vasovagal events, bruising or swelling at site of venepuncture
Bronchodilators	Tachycardia, tremor, cough, nausea, headache
Methacholine test	Headaches, throat irritation, light headedness, chest tightness, breathlessness cough, wheezing
Sputum Induction	Nausea, vomiting, salty taste, wheeze, breathlessness, cough

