#### *9.2.2. Primary Endpoint*

The primary endpoint in this study will be the change from baseline in 24-hour cough frequency (geometric mean) after 14 weeks of intervention over placebo (day 98, visit 8) adjusted for baseline cough frequency (day 13, visit 2). The primary efficacy endpoint will be analysed using a generalised estimating equation modelling (GEE) analysis including the baseline cough frequency as a co-variate. Both FAS and PPS populations will be analysed.

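### A poor-quality cough recording may be repeated at week 8 but not at baseline or week 14, the two recordings that form the primary endpoint

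*Combined protocol and SAP*

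**What the plan says.** Section 9.2.2 defines the primary endpoint as the change in 24-hour cough frequency "after 14 weeks of intervention over placebo (day 98, visit 8) adjusted for baseline cough frequency (day 13, visit 2"). The week 8 recording, made at Visit 5, serves the secondary outcomes (Sections 7.2 and 9.2.3).

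Section 5.10.2 gives a repeat rule at each visit where the monitor comes back:

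- Visit 3 (returns baseline): a repeat if nothing was recorded "due to recording device malfunction (such as battery or card failure) then the subject will be asked to repeat the recording within 24-48 hours".
- Visit 6 (returns week 8): a repeat if nothing was recorded "due to recording device malfunction or if the recording quality is deemed poor, then the subject will be asked to repeat the recording".
- Visit 9 (returns week 14): "If no recording was obtained during the past 24 hours due to recording device malfunction then the subject will be asked to repeat".

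The timing is the same at all three visits: "the recording within 24-48 hours of prior attempt at recording".

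Sputum induction is done at Visits 3, 6 and 9. Visit 3 also includes the first injection, and Visit 9 the methacholine challenge. Table 5 (Section 8.4) lists cough as a known complication of both tests; the sputum induction entry is "Nausea, vomiting, salty taste, wheeze, breathlessness, cough". The full analysis set (FAS) in Section 9.2.1 requires at least one recording before treatment and one after. Table 1 allows ±3 days at Visits 3, 6 and 9, and its footnote allows recording on a Friday with return on the Monday.

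**The concern.** Three parallel visit descriptions set different criteria for the same event, and the wider criterion applies to the one recording that the primary endpoint does not use. No reason is given. It looks like a clause added in one place and not carried across.

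Two things are at stake. A poor baseline recording threatens both the model covariate and membership of the FAS. A poor week 14 recording removes or degrades the primary observation itself. Section 9.1 randomizes 30 participants so that 15 complete each arm, with no allowance for lost recordings.

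A smaller, related gap is that the text does not say whether a repeat comes before or after the other procedures of the return visit, some of which can provoke cough.

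**Working it through.** **1. The repeat rules side by side**

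| Recording | Use | Returned at | Repeat if nothing recorded | Repeat if poor quality |
|---|---|---|---|---|
| Visit 2, baseline | Primary (covariate and reference) | Visit 3 | Yes | No |
| Visit 5, week 8 | Secondary | Visit 6 | Yes | Yes |
| Visit 8, week 14 | Primary | Visit 9 | Yes | No |

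**2. Does another section fill the gap?** Section 5.11 C describes the monitor and the counting, but gives no repeat rule, quality standard or minimum duration. Section 9.3 deals with spurious data through a sensitivity analysis and possible exclusion of participants. It gives no rule for an unusable recording and no repeat. So the visit texts are the only rule.

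**3. Size, as an illustration.** The plan states no rate of poor recordings, so there is no figure of its own to reproduce. Assume a share p unusable at each of baseline and week 14, independent between visits, with every such recording lost.

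- Usable pair without a quality repeat: (1 − p)².
- With one repeat that fails at the same rate: (1 − p²)².

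| p | No quality repeat | Per arm, of 15 | One repeat | Per arm, of 15 |
|---|---|---|---|---|
| 5% | 0.95² = 90.25% | 13.5 | 0.9975² = 99.5% | 14.9 |
| 10% | 0.90² = 81% | 12.2 | 0.99² = 98.0% | 14.7 |
| 15% | 0.85² = 72.25% | 10.8 | 0.9775² = 95.6% | 14.3 |

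The repeat columns assume that every poor recording is recognised in time, so they are a best case.

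**4. Effect on precision.** Use the log SD of 0.60 from Section 9.1 and an unadjusted comparison, with half-width t(0.975, 2n − 2) × 0.60 × √(2/n):

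- n = 15: 2.048 × 0.60 × 0.365 = 0.449
- n = 12 (about the p = 10% case): 2.074 × 0.60 × 0.408 = 0.508

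The ratio is 0.508/0.449 = 1.13, so the interval is 13% wider. The SD cancels in this ratio, so the result does not depend on the 0.60, or on the power statement in Section 9.1.

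**5. Order and timing of a repeat.** A monitor returned 24 hours after fitting is checked on the day of the return visit. A repeat 24-48 hours after the prior attempt therefore falls on or after that day. Nothing in the Visit 3, 6 or 9 text says whether the other procedures wait.

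With a Friday recording and a Monday return, a failure is found about 72 hours after the attempt began. That is 72 − 24 = 48 hours after it ended. It is past the repeat window on the first reading and at its limit on the second. The protocol does not say which applies.

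**The case against.** The strongest case on the other side is that this is one missing clause, and that the text, read in sequence, already puts the check and the repeat first. Each return visit describes the monitor coming back, then the repeat rule, then the procedures, with the injection last at Visit 3. Section 9.2.2 and Table 1 place baseline on the day before the first injection. Local operating procedures, which Section 5.11 invokes but which are not in the documents, may settle the order. Much of this stands, and it rules out several stronger readings that a reader might infer:

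- **That the protocol leads to a post-dose baseline being analysed.** No text directs a repeat after the injection. A baseline recorded after dosing would fail the FAS requirement, so the consequence would be a lost participant.
- **That the ordering gap is peculiar to the primary recordings.** Visit 6 includes sputum induction under the same window and has the same gap.
- **That procedure-provoked cough would bias the treatment comparison.** Section 5.11.1 reports cough in 25% after methacholine in a cited trial, but describes symptoms as mostly absent or transient, improving within 24 hours, with 0.3% symptomatic in later days. Both blinded arms have the same procedures. Added noise in a few repeated recordings is plausible; a difference between arms has no stated basis.
- **That 10% to 28% of pairs will be lost.** The rates of 5-15% are assumed. A poor recording may be partly usable, and a participant with baseline and week 8 recordings stays in the FAS without a usable week 14 recording.

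A practical objection also stands in part. Recordings are processed by an external vendor (Section 5.11 C), so some quality problems may surface too late to repeat. But Visit 6 already presumes that quality can be judged in time for a repeat, and the same presumption can hold at Visits 3 and 9.

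None of this explains why the criterion differs between the three visits.

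**Conclusion.** The inconsistency is real and rests on the text alone: the poor-quality criterion covers the secondary week 8 recording and omits both primary-endpoint recordings. Followed exactly, the protocol leaves a poor baseline or week 14 recording unrepeated. In a 30-person trial with no allowance for lost data, this is worth correcting before recordings are made.

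The size is unknown. The illustration runs from about 90% to 72% of participants with a usable pair. It depends on assumed failure rates of 5-15%, independence between visits, and complete loss of each poor recording. Baseline adjustment would narrow the intervals in absolute terms.

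The order of a repeat relative to the visit procedures is a gap in the text at all three return visits, and secondary to the main point. The documents do not show that any repeat would be taken after dosing, or that the treatment comparison would be biased.

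**What to change.** 1. At Visits 3 and 9, use the Visit 6 criterion ("or if the recording quality is deemed poor, then the subject will be asked to repeat the recording"), based on a check of the file when the device is returned.
2. At Visits 3, 6 and 9, state that a repeat recording is completed before sputum induction and, at Visit 9, before methacholine.
3. Reconcile the Visit 3 text, Table 1 and the FAS definition, so that a repeated baseline recording is consistent with the requirement for a recording before treatment. How the visit is arranged around the injection is for the sponsor to settle.
4. Reconcile the Friday-to-Monday footnote with the 24-48 hour window, and say whether the window runs from the start or the end of the prior attempt.

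The cost is protocol wording, a file check at each return, and an occasional visit shift of 1-2 days. The ±3-day windows can usually absorb this, although a Monday return already uses two of those days. Problems found only by the vendor will still be missed. No endpoint or sample size changes.

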**5.11. Study procedures**

All study procedures will be conducted by appropriately trained and experienced staff and supervised by a medical doctor familiar with the protocol and the experimental techniques and who will be available at all times. Participants will be asked to refrain from consuming caffeine at least 2 hours prior to each visit, and to refrain from taking any salbutamol 4-6 hours before study visits. All procedures listed will be performed according to local standard operating procedures (SOPs)(Table 1). All data produced from study procedures will be documented on CRFs, which will be considered source documents.

**A. Spirometry:**

During a spirometry manoeuvre, participants are asked to inhale maximally then blow out with maximal force into the spirometer until all air from the lungs has been expelled. The two main physiological measures derived from spirometry are FEV1 and FVC, both expressed in litres. FEV1 is the volume of air exhaled in the first second of forced expiration. FVC is the total volume of air exhaled with maximally forced effort. Volumes will be recorded at body temperature–prevailing atmospheric pressure–water vapour saturation. Spirometry in this study will be performed according to ATS and European Respiratory Society (ERS) standards.

**B. Blood Sampling:**

Blood will be collected from subjects during Visits 1, 3, 4, 6, 7 and 9. At visits 1 blood will be taken to assess for complete blood count for blood eosinophils and to ensure no

other clinically significant liver, electrolyte disorders or infections (HIV, Hepatitis B and C). Blood will be collected at Visits 3, 4, 6, 7 and 9 for complete blood count, liver enzymes, and electrolytes. Blood will be collected at Visits 3 (pre-treatment) and 9 (post-treatment) for total, activated mature eosinophils, eosinophil progenitors (assessed by flow cytometry) and related transcriptomics. Remaining plasma from blood processing and sputum at Visit 1 will be analysed to fully characterise type 2 inflammation.

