#### *Mepolizumab as a treatment for chronic cough in eosinophilic airways diseases*

Mepolizumab is a humanised monoclonal antibody against IL-5, which is currently licensed for treatment in patients with severe uncontrolled exacerbations. Interleukin-5 is a key cytokine controlling eosinophil growth, differentiation, recruitment, activation and survival (25-27). Treatment with mepolizumab results in a reduction in serum eosinophils and sputum eosinophils (28, 29). The main clinical benefits are in the reduction in exacerbations requiring treatment bursts of oral corticosteroids (OCS) and/or hospitalisations by approximately 50-60% (29, 30). There have been no studies which have recruited patients with chronic cough or assessed objective cough frequency as a study outcome with anti-IL5 therapy.

Therefore, the aim of this study is to evaluate the effectiveness of mepolizumab for the treatment of chronic cough in patients with eosinophilic airways disease, including both asthma and NAEB.

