### **5.13. Blinding and Randomization**

Subjects will be assigned to one of the two possible treatment arms generated by a computer-generated randomisation schedule prepared by McMaster University, with a ratio of 1:1, mepolizumab or placebo. As there is a known imbalance in the prevalence and cough rates, the study will include sex as a randomisation factor. This will mitigate the possibility of the intervention being confounded by sex differences in the 2 arms of the study. Blinded study drug supplies will be provided in sequentially numbered identical syringes in accordance with the randomisation schedule and dispensed by a pharmacist who shall not be delegated any other role in the study. Subjects, investigators, research staff (with the exception of the pharmacist) and the sponsor will be masked to the treatment sequence assignment. A sealed code-break envelope for each subject containing details of the treatment allocated will be kept in a locked safe at the study site.

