## 6. Investigational Product

### 6.1. Formulation

All investigational products will be manufactured in accordance with Good Manufacturing Practice (GMP). Mepolizumab and placebo will be supplied by GSK in 1ml pre-filled syringes (Table 2). Mepolizumab 100mg or a normal (0.9%) saline placebo subcutaneous injection will be administered at the study centre on days 0, 28, 56 and 84 during the 12 week treatment period. The placebo will have an appearance identical to that of the study drug. Those administering treatment, any study staff involved in subject evaluations, and the subjects will remain blind to treatment assignment for the duration of the study.

**Table 2.** Intervention, dose, form, strength, and manufacturer per intervention.

Intervention	Dose	Form	Strength	Manufacturer
Mepolizumab	100mg	pre-filled (1ml) solution in syringe	100 mg/ml	GSK
Placebo - 0.9% normal saline	N/A	pre-filled (1ml) solution in syringe	N/A	GSK

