## **11. Direct Access to Source Data/Documents**

Source documents are considered to be all information in original records and certified copies of original records of clinical findings, observations, data, or other activities in a clinical study necessary for the reconstruction and evaluation of the study. The investigator will provide direct access to source documents and/or source data in the facilitation of trial-related monitoring, audits, review by REB, and regulatory inspections.

The investigator/institution will maintain adequate and accurate source documents and trial records that include all pertinent observations on each of the site's trial participants. Source data will be attributable, legible, contemporaneous, original, accurate, and complete. Changes to source data will be traceable, not obscure the original entry, and be explained if necessary.

The study will be monitored according to the Sponsor's monitoring plan to ensure that it is conducted and documented properly according to the protocol, GCP, and all applicable regulatory requirements. Monitoring visits will be outlined in the study monitoring plan. The PI will assure she and adequate site personnel are available throughout the study to collaborate with clinical monitors. Clinical monitors must have direct access to source documentation in order to check the completeness, clarity, and consistency of the data recorded in the eCRFs for each participant.

The investigator will make available to the clinical monitor all source documents and medical records necessary to review protocol adherence and eCRFs. In addition, the investigator will work closely with the clinical monitor and, as needed, provide them appropriate evidence that the study is being conducted in accordance with the protocol, applicable regulations, and GCP guidelines.

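### Post-dose eosinophil results are recorded with no step to keep them from people who must stay masked

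*Combined protocol and SAP*

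**What the plan says.** - **Effect on the marker.** Section 1.2 states: "Treatment with mepolizumab results in a reduction in serum eosinophils and sputum eosinophils". It gives no size or variability. Section 2 makes this fall the mechanism under test.
- **Blood.** Section 5.11.B: "Blood will be collected at Visits 3, 4, 6, 7 and 9 for complete blood count, liver enzymes, and electrolytes". The Visit 1 sample in the same section is a "complete blood count for blood eosinophils", so this test yields the eosinophil count. Visit 3 is the baseline: "Blood will be collected at Visits 3 (pre-treatment) and 9 (post-treatment) for total, activated mature eosinophils".
- **Sputum.** Section 5.11.E sends induced sputum for a differential cell count. Table 1 places induction at Visits 1, 3, 6 and 9.
- **Recording.** Section 5.11: "All data produced from study procedures will be documented on CRFs, which will be considered source documents". Section 11: "The investigator/institution will maintain adequate and accurate source documents and trial records that include all pertinent observations". Section 11 also gives clinical monitors direct access to source documents.
- **Masking.** Section 5.13: "Subjects, investigators, research staff (with the exception of the pharmacist) and the sponsor will be masked to the treatment sequence assignment". Section 6.1 adds those who give the injections, and says that "any study staff involved in subject evaluations, and the subjects will remain blind to treatment assignment for the duration of the study".
- **Masking measures.** Sections 5.13 and 6.1 describe identical syringes, a placebo of identical appearance, a pharmacist with no other role, and sealed code-break envelopes. None concerns laboratory results.

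**The concern.** Identical syringes mask the injection but not a laboratory value that the drug is expected to move. The plan measures that value before and repeatedly after dosing, and places it in a record kept by people who must not know the arm. No step withholds, delays or reroutes it.

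At stake are the parts of the trial that depend on a person's report or judgement:

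- The LCQ, modified Borg and cough severity VAS scores, if staff cue participants or share results with them.
- The judgement that a participant has an upper respiratory infection, which leads to withdrawal (5.14). The full analysis set needs a recording after treatment (9.2.1). A withdrawal before the Visit 5 recording therefore removes the participant from it, and a later one can cost the week 14 value.
- Major-deviation calls that decide per-protocol membership (9.2.1).
- The request to repeat a recording judged to be of poor quality at Visit 6 (5.10.2).
- Decisions on which data are spurious, after which participants may be dropped from the primary efficacy set (9.3).

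With 15 participants planned per arm, a few such decisions could move an estimate.

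**Working it through.** **1. Which results are post-dose.** The first injection is at Visit 3, after the baseline samples.

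| Visit | Blood count | Sputum differential | LCQ, Borg, VAS |
|---|---|---|---|
| 3 (baseline) | yes | yes | yes |
| 4 (week 4) | yes | no | yes |
| 6 (week 8 + 1 day) | yes | yes | yes |
| 7 (week 12) | yes | no | yes |
| 9 (final) | yes | yes | yes |

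There are four post-dose blood counts and two post-dose sputum differentials. The Visit 9 samples accompany the last questionnaires and follow the Visit 8 recording. Hence at most three blood counts (Visits 4, 6, 7) and one sputum differential (Visit 6) precede the final assessments. Only the Visit 4 count precedes the Visit 5 recording. Post-dose flow-cytometry eosinophil results come from Visit 9 alone.

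**2. Search for a safeguard.** Sections 5.10, 5.11, 5.13, 6.1, 9, 10 and 11 contain no rule that suppresses eosinophil values, assigns them to an unmasked reader, or holds them until database lock.

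**3. How much one count reveals.** The plan gives no figure to reproduce, so both inputs are assumptions:

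- fall on mepolizumab relative to placebo, r: 50%, 70%, 90%;
- SD of the log ratio of post-dose to Visit 3 count, s: 0.4, 0.6, 0.8, equal in both arms.

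For two normal distributions separated by −ln(1 − r) and a cut-off midway, the share classified correctly is Φ(d/2), with d = −ln(1 − r)/s. Chance is 50%.

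Example: r = 70%, s = 0.6. Then −ln(0.3) = 1.204, d = 1.204/0.6 = 2.007, and Φ(1.003) = 84%.

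| Assumed fall | s = 0.4 | s = 0.6 | s = 0.8 |
|---|---|---|---|
| 50% | 81% | 72% | 67% |
| 70% | 93% | 84% | 77% |
| 90% | 99.8% | 97% | 92% |

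With weaker assumptions (30% fall, s = 0.9), −ln(0.7) = 0.357, d/2 = 0.357/1.8 = 0.198, and the share is 58%.

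**4. Several counts.** Averaging the three counts at Visits 4, 6 and 7, with an assumed correlation of 0.5 between changes, multiplies s by √[(1 + 2 × 0.5)/3] = 0.816. At s = 0.6 the effective SD is 0.49. The shares become Φ(0.693/0.98) = 76%, Φ(1.204/0.98) = 89% and Φ(2.303/0.98) = 99% for falls of 50%, 70% and 90%.

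**5. Limits of the model.** It assumes a reader who knows the best cut-off, and it has no floor. Entry requires sputum eosinophils of at least 2% and sets no blood threshold (5.6), so some participants may start with a low blood count, where a fall is hard to see. For them the shares above are too high.

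**The case against.** The strongest reply is that the gap is one of silence. Section 5.11 says that results are documented, not who opens them or when, and it defers to local procedures that might already hide the differential. This stands as a limit on what can be claimed. It does not close the gap, because the protocol imposes masking and never mentions such a procedure.

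A reader might infer that the blind fails, or that the same staff see the counts, inject, collect scores and make every decision. The documents do not support either. A study physician injects, but no section assigns the questionnaires or the laboratory reports to named roles. Reading a count is also a probabilistic inference and not a code break.

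A reader might also infer that the primary endpoint is biased. The text largely speaks against this:

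- Coughs are counted from audio by software and an external central analyst (5.11.C), although the protocol does not say that this analyst is kept from laboratory data.
- At Visit 9 a repeat recording is triggered only by device malfunction. The poor-quality trigger is written for Visit 6 only.
- Prednisone for an asthma exacerbation (6.7) does not change full-analysis-set membership, which ignores protocol adherence.

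Finally, the scores are completed by participants, and nothing says that they are told their counts. At Visits 4 and 7 blood is drawn at the same visit, so that day's result need not be known when the forms are filled in. This weakens the route to the scores but does not remove it, since earlier results can be known by then. The other judgements listed do not depend on the participant knowing the arm.

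**Conclusion.** The point holds as a gap in the masking procedures. The protocol requires masking throughout, names a marker that the drug lowers, records it after dosing at four visits in blood and two in sputum, and provides nothing to keep it from the people who must stay masked.

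The size is uncertain because the documents give no inputs. On assumed falls of 50-90% and an SD of log change of 0.4-0.8, one count identifies the arm for about 67% to nearly 100% of participants. The share is lower with a smaller or more variable fall, or a low baseline count. These figures describe what a reader of the results could infer. They do not show that anyone reads them, nor how large any bias would be.

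The exposure is mainly in secondary, participant-reported outcomes and in discretionary decisions about withdrawal, per-protocol membership, the Visit 6 repeat and spurious data. The primary cough count is largely protected, but membership of the analysis sets is less so. The change is worth making because it is cheap, and masking lost during conduct cannot be restored at analysis.

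**What to change.** In 5.11.B, 5.11.E and 5.13, state that from the first dose until database lock the following are withheld from subjects, site staff who treat or assess, the sponsor and the cough analyst:

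- post-dose blood eosinophil counts, and the rest of the differential where it would reveal them;
- post-dose sputum differentials;
- post-dose flow-cytometry eosinophil results.

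Other complete blood count values, liver enzymes and electrolytes are released as usual. The sponsor should also state, within existing roles, how a withheld result that needs clinical review is handled. If a local procedure already does this, a sentence citing it is enough.

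Section 13.7 already closes deviations before database lock, so withholding until lock covers the per-protocol calls. It protects the decisions in 9.3 only if spurious data are identified before lock, and 9.3 should say so.

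The cost is protocol and laboratory-manual wording and a change in how results are reported. The documents do not identify the laboratory, so the sponsor must confirm that it can suppress these values and that its readers are outside the masked team. The downside is that the site does not see the post-dose differential in real time. No sample, visit or endpoint is lost.
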